4.4 Assignment of Patients to Treatment Groups

All patients enrolled in this study will be treated with Octaplas. The Investigator will inform the Sponsor of new patients enrolled by the submission of patient entry information.

4.5 Relevant Protocol Deviations

If deviations from the protocol occur, the Investigator should promptly inform the monitor and the nature of the deviation must be reviewed and discussed. Any deviation must be documented, stating the reason and date, the action taken, and the impact for the patient and/or the trial. The documentation must be kept in the Investigator's Trial File and the Sponsor's Trial File. In case of any major protocol deviation the Investigator and the Sponsor will decide on whether the patient should be withdrawn from this study.

4.6 Subsequent Therapy

After the study treatment period has ended, subsequent therapy is at the treating physician's discretion.

5 INVESTIGATIONAL MEDICINAL PRODUCT(S)

5.1 Characterization of Investigational Product(s)

For Octaplas, a new prion affinity column was introduced in the manufacturing process of the product to eliminate potential prion proteins. Furthermore, the time of S/D treatment in the manufacturing process has been shortened from 4–4.5 hours to 1–1.5 hours. These measures increase the concentration of plasmin inhibitor and slightly increase the concentration of protein S compared with octaplas[®].

The virus safety of Octaplas was maintained as shown by virus validation studies. With a total inactivation to below the detection limit, the shortened S/D procedure has a time-safety-margin of >98.3% versus >99.5% for the predecessor product.

5.2 Packaging and Labeling

Octaplas is delivered frozen in sterile, pyrogen free plastic bags containing 200 mL. The bags are vacuum sealed in a clear plastic wrap and delivered in cartons of 10 units.

Each octaplas[™] bag will be labeled as shown below (for blood group A).

NDC 68209-952 – 01

Octaplas[™]

Pooled Plasma (Human), Solvent/Detergent Treated

For intravenous use only.

Rx only.

200 mL contain 9 - 14 g human plasma proteins, 0.88 - 1.48 g sodium citrate dihydrate, 0.06 - 0.24 g sodium dihydrogen phosphate dihydrate, 0.80 - 1.20 g glycine, ≤0.4 mg TNBP and ≤1.0 mg Octoxynol. This product contains no preservative.

Store at ≤-18°C (-0.4°F) protected from light.

Thawed product should be used immediately and must not be refrozen.

Do not use product that is cloudy or has deposits.

Unused product must be discarded.

Caution: New Drug--Limited by Federal (or United States) law to investigational use

Exp. Date:

Lot No.:

U.S. License No. 1646

Manufactured by:

Octapharma AB
[name]
[name]

Distributed by:

Octapharma USA Inc. [name] [contact]
--

Final labeling will comply with the national requirements of each country where the study is to be conducted.

Octaplas is labeled in the United States with the proprietary name octaplasTM. In case the study will be conducted in countries outside of the United States where the product is licensed under the name Octaplas and the product octaplas is recognized as the predecessor product this could lead to mismatch or misunderstanding. Therefore the name Octaplas is used in the current protocol.

5.3 Conditions for Storage and Use

The shelf-life of Octaplas is 36 months when stored at $\leq -18^{\circ}\text{C}$ ($\leq -0.4^{\circ}\text{F}$) and protected from light. After thawing, the product must be used within 24 hours when stored at $1-6^{\circ}\text{C}$ (33.8°F to 42.8°F) or within 8 hours when stored at room temperature 20 to 25°C (68°F to 77°F). See package insert in **Appendix 1**.

The Investigator/authorized personnel at the site will ensure that the product is stored in appropriate conditions with restricted access and in compliance with national regulations.

5.4 Dose and Dosing Schedule

The actual volume of Octaplas administered to a patient will depend on the clinical setting.

If the time interval between the end of one Octaplas infusion and the beginning of the next Octaplas infusion is no longer than 60 minutes, then this will be regarded as 1 infusion episode. If the time interval is more than 60 minutes, this will be counted as 2 different infusion episodes. For patients on CPB who are primed with plasma, a transfusion episode will begin with the initiation of the circuit with plasma and will end when the heparin is reversed during the process of coming off CPB.

The infusion rate of Octaplas should not exceed 0.020-0.025 mmol citrate per kilogram per minute, which is equal to <1 mL Octaplas per kg per minute. This limitation is not applicable for devices used for cardiopulmonary bypass or extracorporeal membrane oxygenation or similar. In case situations like e.g. a serious hemorrhage necessitates a rapid infusion ≥ 1 mL/kg and the benefits outweigh the potential risks, the infusion speed can be ≥ 1 mL/kg body weight. The dose (mL) of Octaplas to be infused will depend on the age and BW of the patient. The first infusion dose will be at a minimum of 10 mL/kg or one unit unless a lesser dose is medically justified. If infusions are performed and the dose administered is less than 10 mL/kg the medical reason justifying this dosage will be recorded in the CRF, since at least 10 mL/kg are required to significantly increase the respective plasma protein levels

5.5 Preparation and Method of Administration

Octaplas will be used per the approved labeling for the product (see **Appendix 1**). Octaplas will be administered based on ABO-blood group compatibility. In urgent cases and in the circumstances that no same blood group is available (type A donor plasma for type A

recipient), patient can be administered plasma that is compatible to recipient's blood group (e.g., donor AB plasma can be administered to recipient with blood group A).

5.6 Blinding, Emergency Envelopes and Breaking the Study Blind

Not applicable. This is an open-label study.

5.7 Treatment Compliance

Drug Dispensing and Accountability

Octaplas will be supplied by the Sponsor. A drug dispensing and accountability log will be kept up-to-date at the Investigator's site, detailing the dates and quantities of the investigational medicinal product (IMP) received at the site and dispensed and administered to each patient. The inventory will be made available to the monitor to verify drug accountability during the study. Unused trial medication will be returned to the Sponsor designated clinical supplies depot or, if approved by the Sponsor in advance, may be destroyed at the Investigator site following local policies for destruction of biologic supplies. Empty bags will not have to be returned and will be destroyed at the study site following local policies after appropriate documentation.

Assessment of Treatment Compliance

Having in mind the setting and the fact that study drug administration will exclusively take place at the investigational site, full compliance is expected.

6 STUDY CONDUCT

6.1 Study Periods

Screening

The following assessments will be performed at Screening:

- Obtaining voluntarily given, written (signed and dated) informed consent by the patient's legal representative(s) or guardian(s). Children deemed old enough by the Investigator/institution to understand the risks and benefits of the study should also be made aware of the risks/benefits of the study and provide written assent. Patients determined to have a reasonable probability to receive intra-operative plasma transfusion according to the Investigator's clinical judgment may also be approached for consent to participate. If these patients are subsequently not prescribed plasma intra-operatively or postoperatively they will be determined to be a screening failure and not included in the analysis.
- Review of inclusion and exclusion criteria.
- Physical examination (see **Section 7.3.6**).
- Relevant medical history including prior medications (taken within 7 days prior to time 0 (study drug given) and on-going concomitant medication(s)).
- Demographic data (height, BW, gender, date of birth, ethnicity).
- Determination of ABO blood group for compatibility.

- Pregnancy testing for females at the age of ≥ 11 or of childbearing potential (if younger than 11 years old). Results must be negative for the female patient to be in the study.
- Documentation of type of surgical procedure indicated for the patient and important operative interventions.
- Ordering of plasma if clinically indicated per physician discretion.

Pre-Infusion (Immediately Before First Infusion Episode)

The following assessments will be performed before the first infusion episode:

- Vital signs (see **Section 7.3.6**).
- Blood sample(s) for hemostatic parameters (see **Section 7.2.1**).
- Blood sample(s) for laboratory parameters (see **Section 7.3.5.3**).

Study Treatment Period

The number of infusion episodes and actual total volume (dose in mL/kg) of Octaplas administered to a patient within the 72-hour treatment period will depend on the clinical setting and physician discretion. After 72 hours from the start of the first infusion of Octaplas, the study treatment period will end. The following procedures will be performed during the study treatment period:

- Administration/infusion of Octaplas.
- Vital signs.
- Monitoring of ADRs (refer to **Section 7.3.2.1** for definition), TEs, TEEs, hyperfibrinolytic events and concomitant medications.
- Pre- and post-infusion episode samples for hemostatic and laboratory parameters will be tested. The pre-infusion episode laboratory samples should be drawn within 6 hours before the start of the first infusion episode and within 60 minutes prior to the start of subsequent infusion episodes. Post-infusion episode samples should be drawn within 30 to 60 minutes after the end of each infusion episode. If the patient requires priming of the cardiopulmonary bypass (CPB) circuit with plasma, the post-infusion episode samples should be drawn 30-60 minutes after reversal of heparin during the process of coming off CPB. For the first infusion episode it is mandatory that pre- and -post-infusion episode laboratory testing is performed. If subsequent infusion episodes are performed, pre- and post-infusion episode laboratory tests should be performed unless considered not medically necessary by the Investigator (e.g., the timing of the pre-infusion episode sample is close to or overlaps with the timing of the post-infusion episode sample and it is not necessary to perform, etc.). In the event pre- or post-infusion laboratory sample(s) are not performed, the reason will be documented in the CRF. If multiple hemostatic and laboratory parameters may be assessed before and/or after the infusion, the hemostatic and laboratory parameters that are assessed closest before the start and after the end of each infusion should be entered in the eCRF.

Safety Follow-up Period

- ADRs, TEs, TEEs, hyperfibrinolytic events and concomitant medications will be monitored for 72 hours (± 6 hours) after the last Octaplas transfusion is completed.

Final Examination

Seventy-two hours (\pm 6 hours) after the end of the last study infusion episode, a Final Examination will be performed that consists of the following assessments:

- Vital signs (see **Section 7.3.6**).
- Physician Assessment of Safety (**Section 7.3.1**).
- Blood sample(s) for laboratory parameters (see **Section 7.3.5.3**).
- Monitoring of ADRs (refer to **Section 7.3.2** for definition), TEs, TEEs, hyperfibrinolytic events and concomitant medications.

After the Final Examination, the clinical phase of the study is considered completed for the patient. No further study-related assessments will be performed, unless safety concerns (e.g., on-going ADRs) require follow-up.

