
¹ An infusion episode is defined as any amount of Octaplas infusion given, with no more than 60 minutes break between 2 Octaplas infusions. If the time interval between the end of one Octaplas infusion and the beginning of the next Octaplas infusion is more than 60 minutes this will be counted as 2 different infusion episodes.

Name of Sponsor/Company: Octapharma Pharmazeutika Produktionsges.m.b.H.	
Name of Investigational Product: Octaplas	Protocol Identification Code: LAS-212
Name of Active Ingredient: Human Coagulation Active Plasma For Infusion, S/D treated	Date of Final Protocol: 19-Nov-2016

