3.2 Overall Study Timeline

The study started in the second quarter 2015 and is planned for completion by 4th quarter of 2017. The end of the study is defined as the last visit of the last patient participating in the study.

Study Flow Chart

Time-Points	Screening/ Pre-Infusion (within 7 days prior to start of first infusion¹)	72-Hour Study Treatment Period (Infusion Episode(s)^{2,3}	72-Hour Safety Follow-up Period ^{3,4}	Final Examination 72 hours after end of last study infusion episode²
Inclusion/Exclusion criteria	X			
Informed consent/assent	X			
Physical examination ⁵	X			
Medical history (incl. prior and current relevant concomitant medications ⁶)	X			
Vital signs ⁷	X	X		X
Documentation of the type of surgical procedure indicated ⁸	X			
Demographic data	X			
Blood group determination	X			
Hemostatic parameters ⁹	X	X		
Laboratory parameters (Chem 7, CBC and ionized calcium) ⁹	X	X		X
Pregnancy test ¹⁰	X			
Ordering of plasma	X			
Administration of Octaplas		X		
Investigator Assessment of Safety ¹¹				X
Monitoring of SAEs and ADRs		←-----Continuously-----→		
Monitoring of TEs, TEEs, and hyperfibrinolytic events (regardless of causality) ¹²				
Monitoring concomitant medication				

1. Screening time window of -7 days does not apply for informed consent/assent procedure.
2. An infusion episode is defined as any amount of Octaplas given, with no more than 60 minutes break between 2 Octaplas infusions. If the time interval between the end of one Octaplas infusion and the beginning of the next Octaplas infusion is more than 60 minutes this will be counted as 2 different infusion episodes. For patients on CPB who are primed with plasma, a transfusion episode will begin with the initiation of the circuit with plasma and will end when the heparin is reversed during the process of coming off CPB. The study Treatment Period will end after 72 hours from the start of the first infusion of Octaplas, or after the end of the last infusion episode if the total duration of Octaplas treatment is <72 hours.

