7. Vital signs will include heart rate, respiratory rate, temperature, arterial saturation and blood pressure assessment. Vitals should be assessed within a maximum of 6 hours before the start and 60 minutes after the end of the first infusion episode. All subsequent assessments should be accomplished within 60 minutes before and 60 minutes after each infusion episode. If multiple vital sign assessments are taken within 60 minutes before and/or after the infusion, the vital signs that are assessed closest before the start and after the end of each infusion should be recorded.
8. The type of surgical procedure indicated as well as start and stop dates and times of the procedure, estimated blood loss, use of ECMO and/or CPB will be recorded on the CRF.
9. Pre- and post-infusion episode samples for hemostatic and laboratory parameters will be tested. Pre-infusion samples for the first infusion episode should be drawn within 6 hours prior to the start of the first infusion episode (all the subsequent pre-infusion assessments are to be done within 60 minutes prior the infusion episode). Post-infusion episode samples should be drawn within 30 to 60 minutes after the end of each infusion. If the patient requires priming of the cardiopulmonary bypass (CPB) circuit with plasma, the post-infusion episode samples should be drawn 30-60 minutes after reversal of heparin during the process of coming off CPB. For the first infusion episode it is mandatory that, pre- and post-infusion episode samples for hemostatic and laboratory parameters be tested. If subsequent infusion episodes are performed, pre- and post-infusion episode laboratory tests should be performed unless considered not medically necessary by the Investigator (e.g., the timing of the pre-infusion episode sample is close to or overlaps with the timing of the post-infusion episode sample and it is not necessary to perform, etc.). In the event the pre- or post-infusion laboratory sample(s) are not drawn, the reason for not obtaining the sample(s) will be recorded on the CRF. If multiple hemostatic and laboratory parameters may be assessed before and/or after the infusion, the hemostatic and laboratory parameters that are assessed closest before the start and after the end of each infusion should be entered in the eCRF. TEG with Kaolin activation or ROTEM EXTEM testing should be performed as defined in **Section 7.3.5.3**.

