7.3.6 Physical Examination and Vital Signs

At Screening, a physical examination will be performed.

A physical examination will be performed in accordance with the site's routine procedures. This may include examination of dermatological and lymphatic system, HEENT, respiratory tract, cardiovascular and gastrointestinal system, musculoskeletal system, and neurological system.

Vital signs will include heart rate, respiratory rate, temperature, arterial saturation, and blood pressure assessment. Vitals should be assessed within a maximum of 6 hours before the start of the first infusion episode and within 60 minutes before the start of subsequent infusion episodes, as well as within 30 to 60 minutes after each infusion episode and at the Final Examination. If multiple vital sign assessments are taken before and/or after the infusion, the vital signs that are assessed closest before the start and after the end of each infusion should be recorded.

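### The eCRF rule for choosing among several post-infusion results is not tied to the 30-60 minute window, the infusion episode or heparin reversal, and the SAP has no rule to correct it

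*Protocol*

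**What the plan says.** **Sampling window.** Protocol 6.1 (Study Treatment Period) states: "Post-infusion episode samples should be drawn within 30 to 60 minutes after the end of each infusion episode". For a plasma-primed bypass circuit the 30-60 minutes run from heparin reversal instead. SAP 10 repeats the 30-60 minute window, without the heparin-reversal anchor.

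**Entry rule.** The same bullet in 6.1 begins its last sentence with "If multiple hemostatic and laboratory parameters may be assessed before and/or after the infusion" and then gives the instruction: "the hemostatic and laboratory parameters that are assessed closest before the start and after the end of each infusion should be entered in the eCRF". Note 9 to the Study Flow Chart (Protocol 3.2) carries the same rule.

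**Episode.** Note 2 to the flow chart says: "An infusion episode is defined as any amount of Octaplas given, with no more than 60 minutes break between 2 Octaplas infusions". One episode can therefore hold several infusions. For a primed circuit, note 2 and Protocol 5.4 end the episode at heparin reversal.

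**Vital signs.** Note 7 says "Vitals should be assessed within a maximum of 6 hours before the start and 60 minutes after the end of the first infusion episode" and opens its selection rule with "If multiple vital sign assessments are taken within 60 minutes before and/or after the infusion". Protocol 7.3.6 asks for readings "as well as within 30 to 60 minutes after each infusion episode and at the Final Examination", and its selection rule has no time limit.

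**Analysis.** SAP 5.2 and 11.2 tabulate laboratory values and changes from baseline by time point. Neither section says which result represents a time point when there are several, or what happens to a result outside the window.

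**The concern.** The window says when the sample should be drawn. The entry rule says which result reaches the database. The two use different anchors: the window runs from the end of the episode (or heparin reversal), while the rule runs from the end of each infusion with no minimum delay. A site that follows the rule as written can meet the sampling schedule and still enter another value.

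At stake is whether the recorded post-infusion values mean the same thing across patients. They feed the laboratory part of the primary endpoint (Chem 7, CBC, ionized calcium) and the secondary hemostatic endpoint (INR, PT, aPTT, TEG or ROTEM). A value taken minutes after an infusion, after only part of an episode's dose, or before heparin reversal is a different measurement from the planned one. There is no control group (Protocol 3.3), so no comparator would expose a timing artefact. If a site enters only the closest result, analysis cannot recover the in-window one.

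**Working it through.** The plan states no figure on this point, so there is nothing to reproduce. The check applies the entry rule literally to constructed timings and compares it with a rule limited to the planned window.

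**1. Inputs**
- Window: 30-60 minutes after the end of the episode, or after heparin reversal (Protocol 6.1).
- Entry rule: earliest result at or after the end of each infusion (Protocol 6.1; 3.2 note 9).
- Episode: breaks of up to 60 minutes do not end it (Protocol 3.2 note 2; 5.4).
- The timings below are illustrative, not trial data.

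**2. Cases (minutes)**

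| Case | Set-up | Samples | Literal rule enters | Windowed rule enters |
|---|---|---|---|---|
| A | One infusion, ends at 0 | 10, 45 | 10 | 45 |
| B | Infusion 1 ends at 0; infusion 2 runs 40 to 80; one episode, ending at 80 | 20, 120 | 20 for infusion 1; 120 for infusion 2 | 120 (120 − 80 = 40 after the end) |
| C | Plasma prime ends at 0; heparin reversed at 120 | 15, 160 | 15 | 160 (160 − 120 = 40 after reversal) |

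In A the early result displaces the in-window one. In B the mid-episode result is entered as well as the post-episode one. It would replace that value only if the eCRF had a single place per episode, and the layout is not in the documents. In C the entered result precedes reversal if the end of infusion means the end of plasma flow. It does not if the site takes the end of the episode.

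**3. Infusion versus episode.** The 30-60 minute window lies wholly inside the 60-minute break that keeps an episode open. A sample at 40 minutes becomes mid-episode if plasma restarts at 50 minutes. That comes from the episode definition, but an entry rule keyed to each infusion does nothing to sort such samples out.

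**4. Heparin.** Protocol 7.3.5.3 requires heparinase for TEG when heparin is known or suspected, and warns that otherwise clot formation may fail and fibrinolysis be missed. It makes no similar provision for INR, PT or aPTT.

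**5. Other wording on the laboratory window**
- Synopsis (first statement), Protocol 6.1, 7.3.5.3, the Laboratory Evaluations Flow Chart and SAP 10: 30-60 minutes after each episode.
- Note 9: 30-60 minutes after each infusion.
- Synopsis, for subsequent episodes: up to 60 minutes after the end, with no 30-minute lower limit. A 5-minute sample satisfies that sentence.

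**6. Frequency.** The documents give no rate of unscheduled testing. *Assumption:* tests arrive at random at r per hour, so the chance of at least one in the first 30 minutes is 1 − exp(−0.5r).

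| r per hour | 0.25 | 0.5 | 1 | 2 |
|---|---|---|---|---|
| Chance | 12% | 22% | 39% | 63% |

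This is only the chance that an early result exists. Displacement also needs a separate in-window result for the same parameter, so under this assumption each figure is an upper bound on displacement.

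**The case against.** A reader might infer that the entry rule overrides the window. No passage gives it precedence. It closes a bullet that has just set the window, so several results can be read as several within 30-60 minutes, and then the two sentences agree. That reading is possible, but the text does not state it. The vital-sign rule in note 7 carries an explicit 60-minute limit and the laboratory rule in note 9 has none, so a site has no textual reason to supply one.

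Two other stronger readings are also unsupported. The sickest children might be thought to contribute the earliest values because they are sampled most, but nothing documents this. The vital-sign windows might seem to contradict each other, but they are nested: a reading at 30-60 minutes also satisfies the limit of 60 minutes. They need aligning, no more.

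The consequences are also bounded. No confirmatory test is planned. SAP 5.2 provides patient profiles on a time scale and individual hemostatic plots, so the timing of entered results can be inspected. Under Protocol 7.3.5.3 the investigator judges clinical significance for any out-of-range result, not for one windowed difference. SAP 10 restates the schedule and does not claim that the data met it. All this stands. It limits the effect, but does not settle which result is entered or analysed.

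Finally, the SAP cites Protocol Version 10 of 29-Nov-2017, while the protocol supplied is dated 19-Nov-2016 and foresees completion in the fourth quarter of 2017. The later version may have changed the rule, and a late change to data entry may recover little.

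**Conclusion.** The point holds as a defect in a stated rule, of moderate importance and cheap to correct. Followed literally, the rule can record an early, mid-episode or pre-reversal value in place of, or alongside, the planned one, and the SAP contains nothing that would detect or separate it.

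Its size cannot be given. It depends on how often more than one result exists and on the eCRF layout, and neither is documented. The range under step 6 rests wholly on assumed rates and is not an estimate for this trial. Where only one post-infusion result exists, the entry rule has no effect. Sample size and hypothesis tests are untouched. What suffers is the timing consistency of the descriptive laboratory and hemostatic summaries.

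The conclusion assumes that sites apply the sentence as worded and that the protocol version cited by the SAP retains it.

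**What to change.** **Protocol 3.2 note 9 and 6.1.** Replace the selection sentence, for post-infusion results, with: *Enter the result drawn 30 to 60 minutes after the last infusion of the episode ended or, for a plasma-primed circuit, after heparin was reversed. If several fall in that window, enter the closest. If none does, enter the nearest result after the end, with its sample time.* Entry takes place afterwards, when it is known which infusion was the last.

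**SAP 10 and 11.2.** Use the recorded times to flag out-of-window, mid-episode and pre-reversal results, and summarise them separately from in-window results.

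**Reconcile the windows.** Use one post-episode laboratory window in the synopsis (both statements), note 9, 6.1, 7.3.5.3 and SAP 10, and one vital-sign window in the synopsis, note 7 and 7.3.6.

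**Cost.** Wording in the protocol, eCRF guidelines and SAP, plus a derived timing flag. Some results move to an out-of-window table. Data already entered can be flagged only where sample times were recorded, and the pre-reversal flag also needs the reversal time, which the documents do not list as a separate item. If data collection is over, the SAP flag is the part still worth making.
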